Honey has a rich history of utilisation dating back to ancient times, thanks to its nutritional and therapeutic properties [21]. Honey is produced globally and is primarily composed of carbohydrates, particularly in the form of monosaccharides like fructose and glucose. Honey is enriched with different biological compounds, like flavonoids and other types of antioxidants, which have been suggested to have cardioprotective benefits [22]. It has a lower glycemic index compared to regular sugar, which may result in a slower release of glucose into the bloodstream and potentially have a favourable impact on blood sugar levels [23].

Coffee and tea are either taken plain or sweetened with sugars, such as white sugar or artificial sweeteners. However, the use of natural sweeteners like honey is becoming more and more popular. Research on the possible health impacts of coffee, tea, and honey has been done separately; nevertheless, a significant gap persists in the research regarding the synergistic effects of tea and coffee when sweetened with honey. This study will investigate whether a three-day consumption of coffee and tea sweetened with honey will significantly influence the blood pressure and blood glucose level in healthy young female adults.

Study goals and objectives

Goals

The primary aim of this study is to determine the effect of acute consumption of honey-sweetened coffee, black tea, and green tea on systolic blood pressure, diastolic blood pressure, heart rate, and blood glucose level in healthy female participants.

Objectives

- To determine whether a three-day consumption of honey-sweetened black tea, green tea, and coffee will have an effect on blood pressure in healthy female individuals.
- To determine whether a three-day consumption of honey-sweetened black tea, green tea, and coffee will have an effect on heart rate in healthy female individuals.
- To determine whether a three-day consumption of honey-sweetened black tea, green tea, and coffee will have an effect on blood glucose level in healthy female individuals.

Study design

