The study is an experimental study; specifically, it is a randomized controlled trial that will involve healthy young female adults between the ages of 18 and 26 years. The participants will consume honey-sweetened black tea, green tea, and coffee, or plain black tea, green tea, and coffee, or warm water, one cup a day for 3 days. The study will be carried out in the Physiology Laboratory, University of Uyo, and will be done within the period of July to October 2023. Each participant will fill out a consent form prior to the study, after which the participants will be given the beverages and observed for 60 minutes, during which their blood pressure, heart rate, and blood glucose level will be measured. This procedure will be repeated for the 3 days of the study. Prior to the consumption of the beverages, baseline measurements of blood pressure, heart rate, and blood glucose will be taken. For this study, a minimum of 200 volunteers will be recruited, and out of this, the eligible participants will be selected.

Methodology

The randomized controlled trial will be carried out among female students studying at the University of Uyo. The participants will be randomly grouped as follows:

Group 1 (Control) will be given 250 mL of water.

Group 2 (Coffee group) will be given 2.25 g of coffee per 250 mL of hot water.

Group 3 (Honey-sweetened coffee group) will be given 2.25 g of coffee per 250 mL of hot water with 20 mL of honey.

Group 4 (Black tea group) will be given one tea bag (2 g) per cup (250 mL) of hot water.

Group 5 (Honey-sweetened black tea) will be given one tea bag (2 g) per cup (250 mL) of hot water with 20 mL of honey.

Group 6 (Green tea group) will be given one bag (2 g) per cup (250 mL) of hot water.

Group 7 (Honey-sweetened green tea) will be given one bag (2 g) per cup (250 mL) of hot water with 20 mL of honey.

Study procedure

• Participants will be screened for eligibility criteria and will be provided with informed consent to participate in the study.

• The participants will be divided into seven groups, as specified above, through random allocation.

• After arrival, the subjects will be allowed to rest for 30 minutes. Then, baseline measurements of their blood pressures, heart rates, and blood glucose levels will be taken. This will serve as the 0-minute measurement. The subjects will then be given the standardized drinks according to their groups.

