• Blood pressures and heart rates of the subjects will be measured and recorded 15 minutes, 30 minutes, 45 minutes, and 60 minutes after consumption of the drinks, while blood glucose levels of the subjects will be measured and recorded 30 minutes and 60 minutes after consumption.

• Blood pressure and heart rate will be measured using a digital sphygmomanometer. Blood pressure is measured in millimeters of mercury (mmHg) and recorded with the systolic number first, followed by the diastolic number. Heart rate is measured in beats per minute (bpm).

• Blood glucose level will be measured with a glucometer. Blood glucose level will be measured in mg/dL.

Intervention

Coffee, black tea, green tea, and honey

The coffee that will be used for this study is Nescafé Gold Blend, manufactured by Nestlé Coffee Brand, Nestlé Global, Vevey, Switzerland. The black tea is Lipton Yellow Label Black Tea, manufactured by Lipton Teas and Infusions, Rotterdam, Netherlands, and the green tea is Qualitea Natural Green Tea, packed by Qualitea Ceylon (PVT) LTD, Wattala, Colombo, Sri Lanka. These will be obtained from Market Square, Ibom Tropicana Mall, Uyo, Akwa-Ibom State, Nigeria. Raw dark amber honey produced by Apis mellifera adansonii will be used for this study, and it will be obtained from Vika Farms located in Mbak Etoi, Akwa-Ibom State, Nigeria.

The participants will be given a cup per day for 3 days. A tea cup will be prepared by infusing a tea bag in 250 mL of hot water (95°C for black tea and 80°C for green tea). The infusion will be done for 7-10 minutes with constant stirring. A cup of coffee will be prepared by dissolving 2.25 g of instant coffee in 250 mL of 95°C water with proper stirring.

The water will be allowed to boil and cooled down to a respectful temperature before the addition of either a tea bag or coffee. The beverages will then be allowed to cool to approximately 35 degrees before honey is added and given for consumption. The control group will be given 250 mL of water at 35°C.

Measurement of blood pressure, heart rate, blood glucose

Blood pressure and heart rate will be recorded on the left arm using an automated blood pressure monitor (Shanghai Little Doctor Electronics CO. LTD, Nantong 226007, China). First, the cuff

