will be firmly placed around the arm (biceps). Then the power button will be pressed, and the automatic machine will read the blood pressure through the cuff. The reading will be taken three times, and the average value will be determined.

Blood glucose level will be measured by the oxidase method using a fine test glucometer (Osang HealthCare (Infopia), [name]). Firstly, the fingertip will be cleaned with an alcohol wipe and allowed to dry completely. The glucometer will be turned on, and a test strip will be inserted into the designated slot. A lancing device will be used to gently prick the fingertips of the subjects. The finger will be gently squeezed to help produce a small blood drop. Then the edge of the test strip will be used to touch the blood droplet until the meter beeps or indicates that it has received enough blood. The glucometer will process the blood sample and display the blood glucose level on the screen.

Sample size

The sample size was determined to assess the number of participants required to measure the mean difference between groups. The sample size was calculated using the formula explained by Charan et al. [24].

Sample size = $[2SD^2(1.96 + 0.84)^2] \div d^2$

Where:

SD = standard deviation from previous studies or pilot study

d = effect size- difference between mean values

However, a sample size of 70 will be used in this study based on available funds, equipment, manpower, and data from the literature.

Randomized controlled trial procedures

Recruitment and screening

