To ensure protection of confidentiality, the data will be entered into the study database with no personal identity, and the source documents will refer to participants solely by their study identification number. Access to the data will be restricted to the research investigators. The study database will be securely stored in the central library of the University of Uyo and Faculty of Basic

Medical Sciences library. Additionally, all data will be compiled into a thesis that will not disclose any participant identities or information. Three copies of the thesis will be generated, which will be distributed as follows:

One copy will be submitted to the Faculty of Basic Medical Sciences library for preservation.

One copy will be retained in the Department of Physiology.

One copy will be kept in the University of Uyo library.

Ethics

All data collected during this study will be treated as strictly confidential. The personal information will be anonymized, and any published results will not include identifiable information. Participation in this study is entirely voluntary. The participants have the right to refuse to participate or withdraw from the study. The participants will consent to participate by filling out and signing an informed consent form. The protocol of this study will be submitted to the Akwa-Ibom State Health Research Ethics Committee, Ministry of Health, Akwa-Ibom State, Nigeria, for approval.

Statistical analysis

The results will be presented as mean \pm standard error of the mean (SEM). All data collected from the research will be analyzed using the Microsoft Excel (MS Excel) application and GraphPad Prism Software (Version 8.1). One-way and two-way analysis of variance (ANOVA), as well as Tukey's post-hoc comparison, will be used to determine the significant differences between the mean values. The statistical significance will be accepted at the level of P < 0.05.

Discussion

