The role of diet in maintaining and promoting cardiovascular and metabolic health has long been a subject of scientific investigation and public interest. Among the diverse dietary components, coffee and tea have received attention for their potential health benefits. Their health advantages are primarily derived from their bioactive constituents, particularly polyphenols and caffeine. Honey, a natural sweetener, has been used for ages and has received attention for its ability to decrease blood pressure. It contains bioactive compounds such as flavonoids, which have vasodilating properties.

High blood pressure and elevated blood glucose level are significant risk factors for chronic diseases, including heart disease and diabetes. These conditions have become global health concerns, contributing to substantial morbidity and mortality. While pharmaceutical interventions are commonly used to manage these conditions, there is a growing interest in natural dietary approaches to support health. Coffee, tea, and honey both contain bioactive compounds that may influence blood pressure, blood glucose, and heart rate. Research on the possible health impacts of coffee, green tea, black tea, and honey has been done separately; however, there remains a notable lack of research examining the combined effects of these beverages with honey. This study protocol describes a randomized controlled trial designed to investigate whether a three-day consumption of either coffee, green tea, or black tea sweetened with honey can significantly change some physiological parameters in healthy young female adults.

This research aims to provide significant insights regarding the possible health benefits or risks linked to the consumption of coffee, black tea, green tea and honey-sweetened coffee, black tea,

and green tea. It will specifically focus on their effects on critical physiological factors such as blood pressure, heart rate, and blood glucose level. Understanding these factors is essential for maintaining individual health, as any adverse changes in them can lead to detrimental health consequences. By examining the relationship between these beverages and these vital health indicators, the study seeks to contribute to the broader understanding of dietary influences on cardiovascular and metabolic health.

References

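### The plan does not say that a drink effect means a difference from water, so a group's change from its own 0-minute mean could be reported as one

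*Combined protocol and SAP*

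**What the plan says.** The analysis plan is one short paragraph under Statistical analysis. Its operative sentences are that one-way and two-way ANOVA with Tukey comparisons "will be used to determine the significant differences between the mean values", and "The statistical significance will be accepted at the level of P < 0.05". It names no factors, no repeated-measures structure, no contrasts and no role for baseline.

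Other sections bear on how this is read:

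- **Study procedure.** Of the pre-drink reading: "This will serve as the 0-minute measurement". Blood pressure and heart rate are then "measured and recorded 15 minutes, 30 minutes, 45 minutes, and 60 minutes after consumption of the drinks", and glucose at 30 and 60 minutes. Study design repeats this on three days.
- **Objectives.** The first asks whether the sweetened drinks "will have an effect on blood pressure in healthy female individuals". The heart rate and glucose objectives have the same form. None says compared with what.
- **Discussion.** The question is whether three days of a sweetened drink "can significantly change some physiological parameters in healthy young female adults". Again there is no comparator.
- **Sample size.** The calculation concerns the number of participants "required to measure the mean difference between groups".
- **Methodology.** Group 1 is a water control. All groups follow the same measurement schedule.

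**The concern.** A test of a group's later mean against its own 0-minute mean is not a randomised comparison. Its null hypothesis is that nothing changes over the hour, not that the drink does nothing. After baseline every participant, water drinkers included, stays under observation for a further hour, has 12 more cuff readings (three at each of four times) and two more finger pricks, and comes back on later days to a setting that has become familiar. Any change these produce is shared by all seven groups. Only a comparison with water removes it.

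The plan lets such a test count because a significant difference between two time means of one group meets the wording of the analysis sentence and appears to answer the objectives as phrased. Two wrong conclusions could follow:

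- A drink with no effect is reported as changing blood pressure, heart rate or glucose.
- A change that is significant in a sweetened group but not in the plain or water group is read as a honey effect, although those groups were never compared.

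A participant term, a multiplicity correction or a baseline covariate does not turn a within-group test into a test of the drink. More precise measurement makes shared drift easier to detect.

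**Working it through.** **Inputs from the documents.** Seven groups; total 70; five blood pressure times per day (0, 15, 30, 45, 60 minutes); significance at 0.05. The Sample size section gives the formula 2·SD²·(1.96 + 0.84)²/d² but no value for SD or d, so 70 cannot be reproduced from it. Equal allocation is not stated; 70/7 = 10 per group is assumed.

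**Which pairs the open wording covers.** Groups by times gives 7 × 5 = 35 means for one outcome on one day, hence 35 × 34/2 = 595 pairs:

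- different groups, same minute: 5 × 21 = 105
- same group, different minute: 7 × 10 = 70
- different group and different minute: 420

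Only the 105 are randomised comparisons at a common time.

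**Assumed values (none is in the documents).** Between-person SD 8 mmHg, within-person SD 4 mmHg, no drink effect, and a drift of 3 mmHg by 60 minutes in every group including water, reached as 0, 0.5, 0.8, 0.95 and 1.0 of the final value.

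**Smallest within-group difference that Tukey declares significant**, q·√(error variance/10):

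1. Participant term, Tukey over five times in each group (252 df, q = 3.886): 3.886 × √(16/10) = 4.92 mmHg.
2. Participant term, Tukey over all 35 means (252 df, q = 5.47): 5.47 × √(16/10) = 6.92 mmHg.
3. No participant term, five times (error variance 64 + 16 = 80; 315 df, q = 3.88): 3.88 × √(80/10) = 10.97 mmHg.

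The difference between two time means in one group has standard error √(2 × 16/10) = 1.79 mmHg. With a true 60-minute drift of 3, the thresholds lie (4.92 − 3)/1.79 = 1.07, (6.92 − 3)/1.79 = 2.19 and (10.97 − 3)/1.79 = 4.45 standard errors above the drift. This is why the three models behave so differently.

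**Simulation, 4000 trials per setting.** Chance that at least one of the six drinks differs significantly from its own 0-minute mean:

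| Analysis | 3 mmHg shared drift |
|---|---|
| Participant term, Tukey over five times in each group | about 83% |
| Participant term, Tukey over all 35 means | about 18% |
| No participant term, Tukey over five times | about 0% |
| Drink-minus-water change, Tukey over seven groups | about 2% |

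**Sensitivity.**

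- First row: 51% at 2 mmHg and 98% at 4 mmHg. At 3 mmHg, 98% if the within-person SD is 3 and 51% if it is 6. With no drift it is already 12%, because six groups are each tested separately.
- Second row: 5% at 2 mmHg.
- Third row: 0.2% at 4 mmHg; 0.5% at 3 mmHg with within-person SD 6.
- Under the first-row model at 3 mmHg, at least one drink is significant while water is not in 60% of trials (51% at SD 3, 46% at SD 6).

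**Second set of assumptions.** Total SD 1, within-person correlation 0.5 to 0.8, linear shared drift of 0.5 SD. Within-group Tukey flags at least one drink in 64–97% of trials when time is a repeated measure and in 4–14% when it is not. Change from 0 to 60 minutes against water flags one in 1.5–1.9%, and the group-by-time test rejects in about 5–6%.

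All of this is one outcome on one day. Four outcomes and three days would add comparisons.

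**The case against.** The strongest reply is that the plan contains no rule that within-group changes count. It is a randomised controlled trial with a water group on the same schedule, and its one statement about a comparison of means outside the analysis paragraph concerns groups. Labelling the baseline as minute 0 names a time point; the value could equally serve for change scores. The Discussion sentence is not a decision rule. The 30-minute rest before baseline should also limit early settling.

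Most of this stands. A reader might infer that the plan prescribes tests of each group against its own 0-minute mean, or treats every significant pair as a finding. The documents do not say so; that would be a conclusion drawn from silence, and the design leans the other way. A reader might also take 83% as the trial's false-positive rate. It is not. It requires a participant term and a Tukey family of five times within each group, neither of which is stated, and an assumed drift and SDs. Under an ordinary two-way ANOVA with the same inputs the risk is close to nil.

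The reply does not close the gap. The Sample size section describes how many participants are needed, not which tests are decisive. The low figure without a participant term comes from an error term that ignores the repeated readings on each person; moving to a repeated-measures model would expose the problem rather than cure it.

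**Conclusion.** The concern holds as an omission that leaves a non-randomised comparison open, not as an error the plan commits. The decisive contrast, the use of the 0-minute value and the comparator are all unstated, so a shared change over minutes or days could be reported as a drink effect.

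Its size cannot be fixed from the documents, which give neither an SD nor a drift. Under the assumptions above it runs from about 0% to about 83% at 3 mmHg, depending on the model, while the comparison of change with water stays near 2% whatever the shared drift. The span shows that the conclusion could turn on a choice not yet made, which is reason to settle it before the data are analysed.

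**What to change.** In Statistical analysis, replace the open sentence with a rule to this effect:

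- An effect is concluded only from between-group contrasts: each drink minus water (six), and each sweetened drink minus the same drink unsweetened (three).
- The contrasts come from a repeated-measures model of the post-drink values, with a participant term and the same day's 0-minute value as a covariate.
- Changes within a group over minutes or days are descriptive only.
- A result that is significant in one group and not in another is not evidence that the groups differ.

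Name the same comparators in the three objectives and in the Discussion sentence.

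The check above used change from 0 minutes. The covariate form makes the same randomised comparison but was not simulated separately.

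The cost is wording: no new participants, visits or measurements. The sponsor should confirm that the named software fits the model, and name another package if it does not. The downside is that significant within-group changes can no longer be reported as findings.

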
 Type
 2
 Diabetes.
 Research
 Journal
 of
 Pharmacognosy.,
 2024,
 11(3),
 31-40.

 10.22127/RJP.2024.418824.2239

23. Saha S. Honey-the natural sweetener become a promising alternative therapeutic: a review.South Indian Journal of Biological Sciences 2015; 1(2): 103.

24. Charan, J., & Biswas, T. How to calculate sample size for different study designs in medical research?. Indian journal of psychological medicine., 2013, 35(2), 121–126. https://doi.org/10.4103/0253-7176.116232

PARTICIPANT ELIGIBILITY QUESTIONNAIRE

Personal information

1. What is your name?

- 2. Gender? M / F
- 3. How old are you?

[] Less than 18 years [] 18-26 years [] 26 years and above

- 4. Weight: _____
- 5. Height: _____
- 6. Phone number:

Medical history

- 7. Do you have a history of hypertension (high blood pressure)? (Yes/No)
- 8. Do you have a history of diabetes or impaired glucose tolerance? (Yes/No)
- 9. Do you have any cardiovascular problem? (Yes/No)

If yes, please specify:

10. Are you on any medication? (Yes/No)

If yes, please specify the medication(s):

Lifestyle

- 11. Do you smoke? (Yes/No)
- 12. Do you consume alcohol? (Yes/No)
- 13. Are you currently following any specific diet plan? (Yes/No)

If yes, please provide details:

Dietary Habits

14. How often do you consume coffee/black tea/green tea?

[] Daily [] Several times per week [] Occasionally [] Rarely/Never

15. Do you regularly consume honey as a sweetener? (Yes/No)

16. Do you have any known allergies or intolerances to any of the following? (Yes/No)

[] Honey

- [] Coffee
- [] Black tea
- [] Green tea

General Health

17. Have you been diagnosed with any chronic medical conditions? (Yes/No) If yes, please provide details:

- 18. Are you currently pregnant or breastfeeding? (Yes/No)
- 19. Have you undergone any recent surgeries? (Yes/No)

If yes, please specify:

20. Are you willing to comply with the study protocol, including the consumption of the assigned tea for the specified duration? (Yes/No)
